3.1.3 Protocol Deviations

Protocol deviations will be recorded and will be classified as under the following categories:

- Did not fulfill eligibility criteria
- Met discontinuation criteria but continued IP treatment
- Received incorrect IP/dose
- Received prohibited concomitant medication
- Protocol-required procedure not adhered to
- Other (GCP deviations, SAE reporting deviations)

The complete specific criteria defining any protocol deviations will be agreed prior to unmasking the study. All protocol deviations will be listed and the number (%) of subjects will be summarized by treatment groups for each category for major protocol deviations.

3.2 Analysis Populations

The analysis populations are defined in Table 3.2-1. The number of subjects (without percentage) by stratification group and treatment group will be tabulated for each of these analysis populations.

Table 3.2-1 Analysis Populations	
Population	Description
Intent-to-treat (ITT) population	Subjects who are randomized and receive any IP will be included in the ITT population to be analyzed according to their randomized treatment group regardless of whether subjects receive an IP different from that they were randomized to.
As-treated population	Subjects who receive any IP will be included in the as-treated population, analyzed according to treatment received. Specifically, subjects randomized to MEDI-551 who received all placebo doses will be included in the placebo group; conversely, subjects randomized to placebo who received at least one dose of MEDI-551 will be included in the active treatment group.
Open-label population	Subjects who receive at least one dose of MEDI-551 during the OLP will constitute this population.
Any MEDI-551 population	Subjects who receive at least one dose of MEDI-551 (either in the RCP or OLP).
Non-OLP population	Subset of as-treated population who do not roll over to OLP

Table 3.2-2 provides an overview of different type of analyses (demographics, safety and efficacy) by analysis populations and study periods.

Table 3.2-2 Overview of Analysis Domains by Analysis Populations and Study Periods

Period	Population				Any MEDI-551
	ITT	As-Treated	Non-OLP	Open-label	
RCP	
 Demographics/ Baseline characteristics Subject disposition Medical and disease history Physical/Neurological Examination Prior and concomitant medication, steroid tapering Efficacy, Rankin scale HCRU, SF-36, Pain 	
 Exposure to investigational product Adverse events C-SSRS Safety Lab/Flow cytometry lab/IgG Immunogenicity Vital sign, weight, ECG 	---	
 Demographics/Baseline characteristics Medical and disease history Physical/Neurological Examination Prior Medication 
The information is based on baseline of RCP but will be presented only for Open-label population
	
SFP	---		
 Subject disposition Concomitant medication Adverse events C-SSRS Flow cytometry lab/IgG Immunogenicity Vital signs 		
OLP		---		
 Subject disposition Concomitant medication Efficacy, Rankin scale HCRU, SF-36, Pain Exposure to investigational product Adverse events C-SSRS Safety Lab/Flow cytometry lab/IgG 	

Table 3.2-2 Overview of Analysis Domains by Analysis Populations and Study Periods

Period	Population				Open-label	Any MEDI-551
	ITT	As-Treated	Non-OLP			
Any MEDI-551 exposure			---	• Vital sign		
 • Exposure to investigational product • Adverse events

3.3 Study Subjects

3.3.1 Subject Disposition and Completion Status

A summary of subject disposition will be presented using the categories presented in Figure 3.3.1-1:

In addition, number of subjects randomized by country and study site will be tabulated. A Kaplan-Meier (KM) curve of the time to study discontinuation will be provided. Number (%) of deaths (along with the reasons) will be reported.

[figure not shown]

Figure 3.3.1-1 Subject Disposition

3.3.2 Demographics and Baseline Characteristics

The following demographics and baseline characteristics will be summarized for Intent-to-Treat (ITT) population by stratification factor and treatment groups as described in Section 3.1.

3.3.2.1 Demographics

- Age (years)
- Age category (< 65, ≥65 years)
- Sex (Male and Female)
- Race (American Indian or Alaskan Native, Asian, Black or African American, Native Hawaiian or Other Pacific Islander, White, Other)
- Ethnicity (Hispanic vs non-Hispanic).
- Region (US vs Non-US) and (Japan vs non-Japan)
- Height (cm)
- Weight (kg)
- BMI (kg/m²)
- BMI category (< 18.5, 18.5-24.9, 25.0-29.9, ≥ 30)

3.3.2.2 Baseline Characteristics

Table 3.3.2.4-1 provides the list of baseline characteristics to summarize along with type of summary.

3.3.2.3 Physical Examination

Presence of abnormal physical examination finding by body system will be listed only as these are collected only at an Assessment Visit.

3.3.2.4 Neurological Examination

Presence of significantly abnormal neurological finding will be summarized by Number (%) of subjects in each category for ITT population.

Table 3.3.2.4-1 Baseline Characteristics

 Type of original diagnosis [NMO, NMOSD] - n (%) Disease duration (years) defined as the years between date of diagnosis and date of 1st administration of IP, calculated as (date of 1st IP administration - date of diagnosis + 1)/365.25 - descriptive statistics Disease duration category (< 5 years, ≥ 5 years) - n (%) Type of 1st relapse [ON, Myelitis, Brain/Brainstem] - n (%) Most recent NMO relapse type prior to 1st IP administration [ON, Myelitis, Brain/Brainstem] - n (%) Number of prior relapse category [1, 2, 3, 4 etc.] - n (%) Annualized relapse rate prior to 1st IP administration, calculated as total number of relapses (irrespective of type) normalized by total person-years; the person-year for each subject will be defined by the time (years) since 1st NMO/NMOSD relapse as defined below - descriptive statistics Time (years) since 1st NMO/NMOSD relapse defined as the years between date of 1st relapse and date of 1st administration of IP, calculated as (date of 1st IP administration - date of 1st relapse + 1)/365.25 - descriptive statistics Annualized relapse rate prior to 1st IP administration based on relapse type reported (ON, Myelitis, Brain/Brainstem) - descriptive statistics Tested for AQP4-IgG prior to randomization (yes/no) - n (%) AQP4-IgG seropositive prior to randomization - n (%) Age (years) at diagnosis- descriptive statistics Age (years) at 1st relapse- descriptive statistics Smoking status Never, Ever - n (%) If ever smoked, current and former but not current - n (%) If former but not current smoker, number of years since cessation - descriptive statistics If current smoker, smoking duration (years) - descriptive statistics If ever smoked, Average number of cigars/day - descriptive statistics Average number of pipes/day- descriptive statistics 	
 EDSS - n(%), descriptive statistics EDSS category [0, 1-5, > 5] - n (%) Functional Systems Scores - n(%), descriptive statistics Monocular visual acuity score [Low and high contrast], left (OS) and right (OD) eye - descriptive statistics Binocular visual acuity score [Low and high contrast] - descriptive statistics Counting Fingers (CF), Hand Movement (HM), Light Perception (LP), No Light Perception/Total Blindness (NLP) - n (%) RAPD (OS), RAPD (OD), No RAPD - n (%) Pupil response score (OD and OS) (1+, 2+, 3+, 4+ and 5+) - n (%) AQP4-IgG titer level based on flow cytometry assay (FACS) Total number of Gd-enhancing lesions, by locations (Brain, Brainstem, Spinal cord, Optic nerve (left and right eye combined)) and overall - descriptive statistics Co-existing autoimmune disease category [Active, Asymptomatic, Remission] (Rheumatoid arthritis, Autoimmune thyroiditis, Celiac disease, Systemic lupus, Sjögren’s syndrome, Insulin dependent diabetes mellitus (IDDM), Myasthenia gravis, Pernicious anaemia, Other) - n(%) Modified Rankin scale (mRS) score (0, 1, 2, 3, 4, 5/6) - n (%) Worst Pain level during past 24 hours (eyes, upper back, lower back, arms, and legs) - descriptive statistics SF-36 (4-week recall) domain scores - descriptive statistics Columbia-Suicide Severity Rating Scale (C-SSRS) categories (see Section 3.7.4.1 for definition) for both lifetime and baseline (past 6 months) - n (%) Chest X-ray [normal, abnormal] - n (%) Vital signs (see section 3.7.4.2) - descriptive statistics, n (%) Electrocardiogram (ECG) (see section 3.7.4.3) - descriptive statistics, n (%) TB test results [Positive, Negative, Indeterminate] - n (%)
--	---

Table 3.3.2.4-1 Baseline Characteristics

• Average number of packs/day- descriptive statistics• Number of pack-years- descriptive statistics• Current Alcohol consumption status [Yes, No] - n (%)• If current consumer, number of days/week- descriptive statistics	
--	--

3.3.3 Investigational Product Exposure

Descriptive statistics of the investigational product exposure will be presented based on the measures outlined in Table 3.3.3-1.

Table 3.3.3-1 Investigational Product Exposure Summary		
Population (Period)		
As-treated population (RCP only)	Open-label population (OLP only)	Any MEDI-551 population (Any MEDI-551 exposure only)

 Extent of exposure (in days) – descriptive statistics Number of doses [1, 2]-n (%) Dose amount (mg) – descriptive statistics Dose amount adjusted for weight (mg/kg) based on most recent weight – descriptive statistics 	
 Extent of exposure (in days) – descriptive statistics Extent of exposure (in days) categories defined by every 26 weeks or 183 day interval – n (%) Number of MEDI-551 doses excluding placebo dose at OLP Day 15 [1, 2, 3, 4, 5 etc. and mean/subject] – n(%) and descriptive statistics Received placebo dose at Day 15 – n (%) 	
 Extent of exposure (in days) – descriptive statistics Extent of exposure (in days) categories defined by every 26 weeks or 183 day interval - n (%) Number of MEDI-551 doses excluding placebo dose at OLP Day 15 [1, 2, 3, 4, 5 etc. and mean/subject] – n(%) and descriptive statistics
Extent of exposure definition		
Last RCP dose date – 1 st RCP dose date + 60 ^a	Last MEDI-551 dose date (OLP) – 1 st OLP dose date + 60 ^a	Last MEDI-551 dose date – 1 st MEDI-551 dose date + 60 ^a
Person-year definition for individual subject ^b		
(Date of last day before OLP or SFP – 1 st RCP dose date + 1)/365.25	(Date of last day before SFP – 1 st OLP dose date + 1)/365.25	(Date of last day before SFP – 1 st MEDI-551 dose date + 1)/365.25
^a based on 5 half-lives		
^b total person-years will be calculated as the sum of the person-years for individual subject		

If entire dose was administered, the dose amount (mg) at a specific visit will be either 0 or 300 mg depending on what treatment the subject had received. If not, the dose will be estimated based on actual volume administered. For example, if a subject receives 175ml (instead of the full 250 mL), the dose amount (mg) will be estimated as $= 300 \times \frac{175}{250} = 210$ provided the subject received MEDI-551.

3.3.4 Prior and Concomitant Medications

Number (%) of subjects who received prior and concomitant medications data will be summarized by AstraZeneca Drug Dictionary (AZDD) preferred term (PT). At each level of summarization, a subject is counted once if he/she reported one or more medications at that level.

3.3.4.1 Definition of prior and concomitant medications

- Prior medications are defined as medications with a start date occurring before the first dose date during RCP.
- Concomitant medications (RCP) are defined:
 - 1) Medications started or stopped on or after first dose date (RCP) and before the first dose of OLP, or
 - 2) Medications started or stopped on or after first dose date (RCP) and before the start of SFP if entering from RCP directly into SFP,
 - 3) Medications started before the first dose date (RCP) and ongoing before the start of OLP, or
 - 4) Medications started before the first dose date (RCP) and ongoing before the start of SFP if entering from RCP directly into SFP.
- Concomitant medications (OLP) are defined as:
 - 1) Medications started or stopped on or after the first dose of OLP and before the start of SFP, or
 - 2) Medications started before the first dose of OLP and did not stop during OLP.
- Concomitant medications (SFP) are defined as:
 - 1) Medications started or stopped on or after the start of SFP, or
 - 2) Medications started before the start of SFP and ongoing during SFP.

The following summary will be provided for the prior and concomitant medications:

- Prior NMO/NMOSD treatment categories separately for acute and maintenance treatment
 - Any immunosuppression (including azathioprine, cyclosporine, cyclophosphamide, methotrexate, mitoxantrone, mycophenolate mofetil, rituximab, corticosteroids for >21 days, or other immunosuppression)
 - Any biologic agent (eg, rituximab, eculizumab, natalizumab)
 - Plasmapheresis
 - IVIg
 - No immunosuppression (except as used to treat acute NMO attacks)
- Concomitant medications excluding rescue medication but including prophylaxis and treatment for infusion related reaction
- Rescue medications including plasmapheresis related to NMO/NMOSD attack or worsening
- Details of plasmapheresis therapy
 - Number (%) of subjects with number of episodes of plasmapheresis therapies (1, 2, 3 etc.) will be summarized
 - Mean number of sessions per plasmapheresis therapy episode (1st therapy, 2nd therapy etc.) will be summarized.

After randomization subjects will receive daily oral corticosteroids (prednisone or equivalent oral glucocorticoid) according to the schedule below during RCP:

- 20 mg on Day 1 through Day 14
- 15 mg on Day 15
- 10 mg Day 16
- 7.5 mg on Day 17
- 5 mg on Days 18 and 19
- 2.5 mg on Days 20 and 21

Descriptive summary on the following will be provided:

- Total corticosteroid (mg) received based on above tapering schedule
- Daily dose (mg/day) per subject

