4.7.1.1 Immunosuppressive Medications During the Screening Period

Subjects that have previously been taking immunosuppressive medications (including but not limited to, AZA and MMF) and steroids not specifically excluded in Section 4.1.3 for the prevention or treatment of NMO/NMOSD relapses may continue to take those medications during the screening period as long as the dose remains stable or decreases.

Immunosuppressive medications must be stopped prior to dosing on Day 1. Steroids must continue according to the protocol (see Section 4.5.2.2).

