2.2 Study Design

2.2.1 Overview

This is a multicenter, multinational, randomized, double-masked, placebo-controlled study with an open-label extension period to evaluate the efficacy and safety of intravenous (IV) MEDI-551 in adult subjects with AQP4-IgG seropositive and seronegative NMO and NMOSD. Following a screening period of up to 28 days, 252 subjects with NMO/NMOSD will be randomized in a 3:1 ratio (stratified by AQP4-IgG serostatus and Japan vs non-Japan origin) to receive IV MEDI-551 (300 mg at Day 1 and 300 mg at Day 15) or placebo for a period of 197 days (RCP).

Enrollment of subjects into the study will stop when a total of 67 AC-determined NMOSD attacks occur, when 252 subjects have been randomized, or following a recommendation by the independent Data Monitoring Committee (DMC) to stop enrollment, whichever occurs first.

Subjects who complete the RCP without experiencing an Adjudication Committee (AC)-determined NMO/NMOSD attack will be given the option to enroll into an OLP and will initiate or continue treatment with MEDI-551. Subjects who experience an AC-determined NMO/NMOSD attack during the RCP will be given the option to enroll into the OLP following rescue therapy. Subjects for whom the NMO/NMOSD attack is not determined by the AC will continue in the RCP until Day 197 (or until an AC-determined attack occurs). Subjects who are in the RCP when a total of 67 AC-determined NMOSD attacks have occurred or subjects who are in the RCP when enrollment is discontinued upon recommendation of the independent DMC based on evidence of efficacy and safety, will discontinue the RCP as soon as possible, preferably within 14 days and be given the option to enroll into the OLP.

The OLP will continue for a minimum of 1 year and a maximum of 3 years after the last subject enters the OLP, or until regulatory approval for MEDI-551 in the participating country, or until the Sponsor discontinues development of MEDI-551 in this indication, whichever occurs first. Subjects can choose to exit the OLP at any time at which point they enter the Safety Follow-up Period (SFP; unless consent is withdrawn).

All subjects will continue in the SFP to evaluate the long-term safety of the investigational product (IP).

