2.2.1.3 Randomized-controlled Period (Day 1 to Day 197)

Following randomization on Day 1, subjects will be treated with 300 mg MEDI-551 or placebo on Day 1 and Day 15. An oral corticosteroid course will be initiated on Day 1 (prednisone 20 mg/day or equivalent oral glucocorticoid) and will continue until Day 14. Tapering the oral corticosteroids will occur from Day 15 to Day 21. By Day 21, tapering must be completed.

During the RCP, subjects will be followed at scheduled study visits and by telephone interview. The planned duration of the RCP for each subject will be 197 days. All subjects completing the RCP without developing an AC-determined NMO/NMOSD attack will be

given the option to enter the OLP. Subjects who are in the RCP when a total of 67 AC-determined NMOSD attacks have occurred ,or subjects who are in the RCP when enrollment is discontinued upon recommendation of the independent DMC based on evidence of efficacy and safety, will discontinue the RCP as soon as possible, preferably within 14 days and be given the option to enroll into the OLP.

Subjects will be monitored for new or worsening symptoms related to NMO/NMOSD during scheduled study visits and with follow-up phone calls every 2 weeks between study visits (or if a scheduled visit is missed).

When a possible new or worsening symptom(s) related to NMO/NMOSD is identified, subjects will be required to inform the site. If an Assessment Visit is deemed necessary, this must be scheduled as soon as possible but within 72 hours of reporting of the symptoms to the site. At the Assessment Visit, subjects will initially undergo evaluations to determine if the symptoms are related to NMO/NMOSD; if related, the subjects will undergo further evaluations to determine if the symptoms meet at least ONE of the protocol-defined criteria for an NMO/NMOSD attack. In cases where a new or worsening symptom(s) does not meet at least one of the protocol-defined criteria for an NMO/NMOSD attack, the subject will continue in the RCP. The data related to the assessment of the symptoms that were determined by the investigator as not related to NMO/NMOSD will be sent to the AC for review.

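### Item 2 of the SAP's OLP concomitant-medication definition admits treatments that ended before the OLP, so the descriptive OLP table would list them as OLP use

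*SAP*

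**What the plan says.** SAP 3.3.4.1 defines concomitant medication separately for each study period. For the OLP there are two alternatives. Item 1 is "Medications started or stopped on or after the first dose of OLP and before the start of SFP, or". Item 2 is "Medications started before the first dose of OLP and did not stop during OLP".

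The corresponding items for the other periods are worded differently. The SFP item reads "Medications started before the start of SFP and ongoing during SFP". The first RCP item for earlier starters reads "Medications started before the first dose date (RCP) and ongoing before the start of OLP, or". Only the OLP item describes carry-over by the absence of a stop in the period.

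The definition feeds a planned output. SAP Table 3.2-2 lists concomitant medication among the OLP analyses for the open-label population. SAP 3.3.4 summarizes by preferred term and counts a subject once per term. Among the summaries in 3.3.4.1, one is "Concomitant medications excluding rescue medication but including prophylaxis and treatment for infusion related reaction"; rescue medication has its own line.

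Three features of the design produce treatments that normally end before the OLP:

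- **Oral prednisone or equivalent**, given to every RCP subject from Day 1: "By Day 21, tapering must be completed" (SAP 2.2.1.3).
- **Background treatment:** "Immunosuppressive medications must be stopped prior to dosing on Day 1" (Protocol 4.7.1.1).
- **Attack treatment:** subjects with an adjudicated RCP attack "will be given the option to enroll into the OLP following rescue therapy" (SAP 2.2.1).

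**The concern.** Item 2 is evidently meant to pick up drugs carried from the RCP into the OLP and taken throughout it. As written, it also picks up drugs that were finished before the OLP began, because they too have no stop date inside it. One old record is enough to put a subject in a preferred-term row.

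What is at stake is the reading of the open-label data. The long-term attack rate has no comparator and is summarized descriptively. A reader will look at the OLP medication table to see what else subjects were taking. A table that mixes completed and current treatment cannot answer that question.

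**Working it through.** The plan gives no figure to reproduce; the check is one of logic.

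**Notation.** Let s be the start date, e the stop date, O the first OLP dose and F the start of the SFP.

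- Item 1: O ≤ s < F, or O ≤ e < F.
- Item 2: s < O, and not (O ≤ e < F).

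**Medications with s < O.** Item 1 holds exactly when e falls in the OLP. Item 2 holds exactly when it does not. One of the two is always true, so every medication started before the OLP is classed as OLP use. Medications started within the OLP enter through item 1. The definition therefore reduces to s < F and excludes only medications first started in the SFP.

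**Test records.** The timeline is assumed for illustration: first RCP dose Day 1, O = Day 197, F = Day 1000. The third column uses item 2 as written; the fourth replaces it with s < O and ongoing at O.

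| Record | Days (start, stop) | As written | Ongoing at O |
|---|---|---|---|
| Azathioprine stopped before RCP dosing | -700, 0 | OLP | not OLP |
| Rituximab, long past | -900, -400 | OLP | not OLP |
| RCP prednisone course | 1, 21 | OLP | not OLP |
| Antibiotic in the RCP | 60, 70 | OLP | not OLP |
| RCP rescue course | 100, 105 | meets the date rule | does not |
| Chronic drug, no stop | -300, none | OLP | OLP |
| Started in RCP, stopped in OLP | 150, 400 | OLP | OLP |
| Started in RCP, stopped in SFP | 150, 1100 | OLP | OLP |
| Started in OLP | 300, 310 | OLP | OLP |

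Every start day from -300 to 196 was also paired with every later stop day up to 1199, and with no stop. As written, the rule classed all of these combinations as OLP use.

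**Comparison with the SFP item.** Under the SFP wording on the same timeline, none of the first five records counts as SFP use. The ongoing condition makes the difference.

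**Who is affected.** The prednisone course is required of all RCP subjects and ends by Day 21. Anyone entering the OLP after that carries a completed record that item 2 admits, so the row for that preferred term would contain nearly all OLP subjects. A subject still taking prednisone at the first OLP dose would be counted correctly. The number of subjects with washed-out immunosuppressants is not given in the documents.

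**The case against.** The strongest reply is that context settles the meaning. The item sits under the OLP heading and complements item 1. Read literally, the definition would select almost nothing out, which no author intends, and a sensible programmer would code carry-over. That is a fair account of intent, and the SFP wording supports it. It does not rescue the text: a pre-specified derivation should give the right answer when followed, and the SAP amendment history records that this definition was revised to reduce ambiguity.

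The reply does limit the consequences. A reader might infer more than the documents support in these respects:

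- **RCP rescue shown as OLP rescue.** Rescue is excluded from the general concomitant table. Its own summary line states no period split, so this follows only if that summary is divided by the same definitions.
- **A size of 67 out of 252 subjects.** This is not a bound. Rescue follows the investigator's judgment whatever the adjudication outcome (Protocol 4.3.1.1). The relevant denominator is the open-label population, not all randomized subjects. Enrollment was also stopped on the DMC's recommendation.
- **Subjects counted as users of prohibited drugs.** No SAP analysis derives prohibited use from this flag. Prohibited medication is a separate protocol-deviation category (SAP 3.1.3). The washed-out drugs would simply be rows in a descriptive table.
- **Corticosteroid use created from nothing.** Intravenous methylprednisolone premedication is required at OLP dosing visits, and the table includes infusion prophylaxis. Corticosteroids would therefore appear for nearly all subjects anyway; only the row for the oral course is spurious.
- **The same fault in RCP items 3 and 4.** Those items already carry an ongoing condition, and no misclassification has been shown there.

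**Conclusion.** The point holds as a wording error in a stated rule. Followed literally, OLP item 2 puts treatments completed before the OLP into the OLP concomitant-medication table. The clearest case is the RCP prednisone row, which would include nearly all OLP subjects; immunosuppressants stopped before RCP Day 1 would also be listed.

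The effect is confined to descriptive OLP medication output. The primary and key secondary analyses, Type I error control and power do not use this definition. The annualized attack rate is built from adjudicated attacks and person-years, so it does not change either.

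The conclusion assumes that the item is programmed as written and that completed treatments are in the database with start and stop dates, as Protocol 4.5.2.2 and 4.7.1 require. If the programmer codes the evident intent, the table is right but does not follow its own definition. The matter is minor and worth correcting because correction is nearly free.

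**What to change.** In OLP item 2, keep the start condition and replace the stop condition with: ongoing at the first dose of OLP. This parallels the SFP item. In the test records it removes every false inclusion and keeps every drug in use during the OLP.

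Determine ongoing from the recorded ongoing status. A missing stop date alone should not be taken as ongoing, or a completed RCP course with no recorded end date would return to the table. Section 3.3.4.1 gives no rule for missing stop dates, and the protocol lists start and stop dates without naming an ongoing indicator. The SAP should therefore say which field is used.

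If the rescue summary is to be presented by period, state that and apply the same definition. RCP items 3 and 4 need no change on this account.

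The cost is one SAP sentence and one condition in the derivation program. No data collection or inferential analysis changes.
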